2.3. Tranexamic acid

6.3.1. Tranexamic acid pharmacology

Tranexamic acid is a synthetic compound derived from the amino acid lysine that is an analog of aminocaproic acid and acts as a fibrinolysis inhibitor. Tranexamic acid works by binding to the five binding sites of the amino acid lysine on plasminogen to inhibit its activation into plasmin which plays a role in fibrinolysis. To inhibit its activation into plasmin which plays a role in fibrinolysis. In addition, tranexamic acid also has an anti-inflammatory profile by inhibiting plasmin-mediated activation of complement, monocytes, and neutrophils. This drug has good absorption with oral administration, an initial dose of 15 mg/kg and a follow-up dose of 30 mg/kg every 6 hours, and is eliminated through the kidneys. Tranexamic acid can also be given intravenously at a dose of 0.5-1 gram three times per day with a dose restriction of 5-10 mg/kg in patients with renal failure.²⁹ The minimum concentration required to inhibit fibrinolysis in vitro is 10 mcg/ml in adults.³⁵ A meta-analysis conducted in 2020 said that tranexamic acid administration did not affect blood clotting time but significantly reduced post-surgical bleeding and transfusion requirements in patients with cardiac surgery.³⁶

This compound is widely used as a prophylactic and therapeutic agent for bleeding, for example, in surgical interventions and severe trauma, thus reducing the amount of perioperative bleeding and the blood products transfusion after cardiac surgery. Early administration of tranexamic acid, primarily via the intravenous route, is known to increase the chances of survival in emergency cases of massive bleeding. Due to its significant role,

the World Health Organization (WHO) included tranexamic acid in the list of essential drugs.³⁷ However, it is contraindicated in patients with disseminated intravascular coagulation and upper genitourinary tract bleeding (kidney and ureter) due to its potential to cause excessive blood clot formation.³⁴

6.3.2. Effect of tranexamic acid on post-open heart surgery outcomes

Tranexamic acid has been widely used in open-heart surgery to reduce bleeding and the need for post-surgical blood transfusions. Guidelines from the Society of Thoracic Surgeons have recommended using tranexamic acid to reduce bleeding from cardiac surgery (class I recommendation).⁹ The anti-inflammatory profile of tranexamic acid also plays a role in addressing the inflammatory response after cardiac surgery, especially for those using cardiopulmonary bypass. This is because cardiopulmonary bypass carries the risk of coagulopathy, including activation of intrinsic and extrinsic coagulation pathways, platelet dysfunction, and systemic inflammatory response.³⁸ Studies show that low-dose tranexamic acid (10 mg/kg intravenously) is the optimal dose for cardiac surgery.³⁹

Despite its benefits in reducing bleeding and inflammation, several unexpected post-surgical side effects have been reported with tranexamic acid as surgical prophylaxis. The antifibrinolytic profile of tranexamic acid theoretically allows for an increased risk of thromboembolic events such as deep vein thrombosis, early occlusion of vascular implants, cerebral and myocardial infarction, and pulmonary embolism.^{9,10} This is in line with Ross and Salman's meta-analysis, which showed that some patients receiving tranexamic acid prophylaxis and aprotinin (a tranexamic acid analog) experienced thromboembolic events at 1.9% (95% confidence interval 1.1-2.9) and 3.0% (95% confidence interval 1.8-4.6), respectively. However, these events occurred in patients undergoing surgery for subarachnoid

hemorrhage.³⁹

Tranexamic acid can cross the blood-brain barrier, with cerebrospinal fluid concentrations reaching about 10% of plasma concentrations. A concentration of as much as 15 micrograms per milliliter has been said to be the threshold for potential excitation effects.³⁵ There have been reported cases of patients experiencing seizures after open heart surgery, especially those receiving high doses of intravenous tranexamic acid.¹⁴ Study by Kalavrouziotis et al. showed that tranexamic acid at doses ≥ 100 mg/kg intravenously was associated with an increased risk of early postoperative seizures in patients undergoing cardiac surgery with cardiopulmonary bypass.⁴⁰ Meta-analysis by Takagi et al. and Guo et al. also showed that adult patients who underwent cardiac surgery and received tranexamic acid therapy had a fourfold risk of seizures.^{41,42} This is thought to be because the molecular structure of tranexamic acid is similar to that of gamma-aminobutyric acid (GABA), an inhibitory neurotransmitter, and thus has an antagonistic effect on its receptors in the central nervous system.⁹

Nonetheless, other studies have looked at this issue and provided different results. Saracoglu et al. presented the results of a retrospective cohort study on 172 subjects who underwent open-heart surgery, received a regimen of 50 mg/kg intravenous tranexamic acid as bleeding prophylaxis, and showed no cases of thrombosis, stroke, or seizure. The number of post-heart surgery reoperations was similar to the group that did not receive tranexamic acid prophylaxis. Reoperation was similar to the group that did not receive tranexamic acid prophylaxis (4.1%).⁴⁴ In addition, a retrospective cohort study conducted by Maeda et al. also explained that discontinuing tranexamic acid for cardiac surgery did not make a significant difference in the incidence of thromboembolism and postoperative mortality. However, there was a decrease in seizures and

increased postoperative bleeding when tranexamic acid was not given.⁴⁵

Although studies to date have shown controversial results regarding the adverse effects of tranexamic acid post-open heart surgery, such outcomes clinically affect the cost and duration of hospitalization and the quality of life for patients who experience adverse events.¹¹ As these events are primarily reported in patients receiving tranexamic acid intravenously, it was thought that the route of administration might influence the risk of postoperative adverse events. Topical administration (intrapericardial in cardiac surgery) is considered a safer alternative as it works locally but is still effective in reducing bleeding and inflammation.¹²

Several studies have compared post-cardiac surgery outcomes on tranexamic acid administration via topical, intravenous, and/or placebo routes, albeit with differing results. Vaněk and Straka's meta-analysis of four randomized controlled clinical trials comparing topical and placebo administration of tranexamic acid in cardiac surgery showed a trend towards decreased bleeding in the group receiving topical tranexamic acid, although not statistically significant.⁴⁶ Randomized controlled clinical trials conducted by Hosseini et al., Shah et al., and Chaudhary et al. showed a statistically significant reduction in the amount of bleeding after open heart surgery in the group receiving topical tranexamic acid compared to placebo.⁴⁷⁻⁴⁹ Similar results were also obtained in the meta-analysis of Montroy et al. and Habbab et al., with no significant difference in the incidence of post-heart surgery seizures and thromboembolism between the topical tranexamic acid and placebo groups.^{13,50} Habbab et al. randomized controlled clinical trial was the first to compare post-cardiac surgery outcomes between topical and intravenous tranexamic acid groups, showing a trend toward decreased bleeding, blood products transfusion after cardiac surgery, reoperation, and incidence of post-surgical seizures in the topical tranexamic acid group.¹²

6.3.3. Comparison of systemic and topical tranexamic acid

Intravenous administration of tranexamic acid has been associated with an increased risk of thromboembolism and early *graft* closure in coronary artery bypass surgery. Reported cases of thromboembolism include cerebral, pulmonary, mesenteric, and retinal thromboembolism. Due to the significant systemic side effects of intravenous administration, topical administration of tranexamic acid has become increasingly popular. This is because the local antifibrinolytic effect facilitated by the topical application of tranexamic acid has proven effective in preventing bleeding in several other disease cases, such as post-oral surgery of patients with hemophilia, epistaxis, bladder surgery, and gynecological bleeding.⁵¹

Topical administration can provide adequate concentrations at the wound site while providing low systemic concentrations.³⁵ Other studies show that topical tranexamic acid in surgery can significantly reduce bleeding and transfusion requirements without increased side effects.^{52,53} This condition may be due to the shallow degree of systemic absorption after topical application compared to intravenous bolus administration. The study stated that topical application of tranexamic acid gave a mean peak serum concentration of 4.9 mcg/mL in the group treated with fluid bolus in the wound cavity and 5.2 mcg/mL in the group treated with moisturizing the wound surface. These levels are lower than the minimum levels required for systemic effects. In addition, at 5 mcg/mL, only 0.5 mcg/mL will cross the blood-brain barrier, making it very unlikely to cause seizures. In contrast, after administration of 1 g of intravenous tranexamic acid, the serum concentration is above 10 mcg/mL for about 2.5 hours.³⁵

Topical administration of tranexamic acid in surgery is generally given as a bolus to the cavity or added to irrigation fluid.³⁵ In a study by De Bonis et al.

100 mL of tranexamic acid solution (1 g in 100 mL of 0.9% NaCl) or room-temperature placebo was poured into the pericardial cavity and mediastinal tissue of patients before sternal closure. The bleeding was measured every hour, every 24 hours, and before discharge. The results showed that 1% tranexamic acid solution applied topically into the pericardial cavity after coronary artery bypass surgery can significantly reduce bleeding in the first 3 hours, with a reduction of 36% in the first 3 hours and 25% in the first 24 hours when compared with placebo. In addition, the study also showed that tranexamic acid could not be detected in blood samples taken 2 hours after the chest tube was opened, indicating that topically applied tranexamic acid can have a topical impact on the pericardial cavity without causing systemic effects, thus preventing the occurrence of feared systemic side effects.⁵¹ However, tranexamic acid should not be applied topically to the central nervous system as it may cause seizures. In addition, topical application of high doses of tranexamic acid may also inhibit glutamate receptors in various tissues. Prolonged exposure to high-dose topical tranexamic acid may prevent nontoxic epithelial reepithelialization and shed in *vivo* human skin wound models.⁵²

There is no literature stating the ideal minimum effective dose of tranexamic acid. However, a meta-analysis study from Ausen et al. explained that a tissue concentration of tranexamic acid of at least 10 µg/mL is required to inhibit fibrinolysis significantly. No study has yet described the topical effect of tranexamic acid determined by the concentration of the drug, the total dose, and/or the combination of concentration and contact time of tranexamic acid with the surrounding tissue.⁵²

6.4. Theoretical framework

[figure not shown]

Figure 2.2. Theoretical framework

6.5 Conceptual framework

[figure not shown]

Figure 2.3. Conceptual framework

CHAPTER 3

RESEARCH METHODS

3.1. Research design

This study used a randomized clinical trial, placebo-controlled and double-blinded.

3.2. Time and place of research

This study occurred from October to December 2022 at the Division of Adult Cardiac Surgery, Harapan Kita National Heart Center Hospital (RSPJNHK).

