1.1. Background

Coronary heart disease is the highest cause of mortality in the world, contributing to 16.6% of deaths in 2016.¹ In Indonesia, 35% of mortality is due to cardiovascular disease, including coronary heart disease.² Coronary artery revascularization plays an essential role in managing coronary heart disease by improving antegrade blood flow to reduce chest pain (angina). Cardiopulmonary bypass machine (CPB) has been used in coronary artery bypass grafting (CABG) surgery for over three decades. CPB machines allow for an adequate operating field without being disturbed by cardiac motion when performing coronary artery anastomosis, making intracardiac and extracardiac procedures easier to perform and potentially improving cardiac surgical services.³ However, CPB machines have many pathological effects, including fluid retention, coagulopathy, the release of inflammatory mediators, pulmonary dysfunction, stroke, and neurocognitive changes. In 2020, coronary artery bypass surgery was one of the most frequently performed procedures at Harapan Kita Heart and Vascular Hospital, with 419 cases. However, some experienced several postoperative complications, such as postoperative bleeding requiring reoperation (24 cases), cardiac arrest (14 cases), atrial fibrillation (11 cases), and stroke within the first 72 hours (5 cases).

The choice of CABG therapy is based on the patient's clinical characteristics, SYNTAX score and the complexity of the coronary anatomy.⁴ One of the CABG techniques, off-pump coronary artery bypass (OPCAB), was the first revascularisation procedure performed on a beating heart in 1960. The OPCAB technique was abandoned until the invention of stabilisation aids and positioning aids that facilitate anastomosis. The OPCAB technique when performed by highly skilled surgical specialists can result in complete revascularisation and better outcomes in patients at high risk, including the elderly, low ejection fraction, high

neurological risk, women, and end-stage organ failure.⁵

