The surgical technique with OPCAB can be considered in high risk patients to reduce perioperative transfusion requirements. This statement is supported by a *randomised controlled trial* (RCT) study in 2359 patients >75 years old at 12 German institutions with funding from the German Off-Pump Coronary Artery Bypass Grafting in Elderly Patients (GOPCABE) which states that the OPCAB surgical technique significantly reduces blood transfusion requirements.³ OPCAB is not completely free from the risk of postoperative bleeding, as blood loss in the OPCAB technique can occur due to mechanisms of activation of the fibrinolysis pathway caused by sternotomy, pericardiotomy, excision of vein and artery grafts, residual heparin, platelet disorders and surgical bleeding.⁶

Management of valvular heart disease includes non-surgical and surgical interventions. Both are classified as class II and III recommendations respectively based on the 2017 *European Society of Cardiology* guidelines due to the limited number of studies involving large numbers of subjects related to valvular heart disease.^{9,12} Surgical intervention is performed in severe, symptomatic cases, and or there is a decrease in left ventricular ejection fraction <50% which can be done openly or transcatheter.⁸ Harapan Kita Heart and Vascular Hospital in 2020 reported 521 patients undergoing heart valve replacement surgery. A total of 158 patients experienced postoperative complications, with the most common complication being bleeding, which was 43 patients.

Massive blood loss is the leading cause of death in cardiovascular surgery. Bleeding from cardiac surgery can be assessed by the volume of *chest tube drainage bleeding* and the need for transfusion of blood components. Based on the guidelines of the Society of Thoracic Surgeons (2011), the use of intravenous tranexamic acid is recommended in cardiac surgery as a strategy to reduce the risk of bleeding (class I recommendation).⁹ Tranexamic acid has an antifibrinolytic profile that could

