1.1.1 Definition off-pump coronary artery bypass grafting

Coronary bypass artery graft (CABG) surgery is the most effective standard treatment for *coronary* heart disease. *Off-pump CABG* (OPCAB) is one of the CABG surgical techniques performed on a beating heart without the aid of a *cardiopulmonary bypass* (CPB) device, requiring high skills to perform this technique so it is not practised as widely as conventional CABG techniques.⁵⁴ In the OPCAB technique, the heart is still allowed to beat so stabilisation aids are required with *octopus* and *suction* aids *starfish* to facilitate position transfer during surgery. The OPCAB technique is an option because it can reduce the incidence of

postoperative complications caused by the use of CPB machines, these complications occur due to the effects of systemic inflammation due to the interaction of blood components with foreign objects, namely the surface of the *bypass* circuit. Complications include post surgical haemorrhage, neurocognitive dysfunction, thromboembolism, fluid retention and organ dysfunction.⁷ In high risk patients OPCAB has lower morbidity and mortality rates, this is due to improved organ perfusion, protection of the myocardium due to minimal manipulation of the aorta, and avoidance of systemic inflammation due to the use of CPB.⁸ Various studies have shown the advantages of OPCAB in reducing transfusion requirements, shorter hospital stay, reduced ICU and ventilator requirements, and more affordable costs.⁵⁵

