3.3. Research population

The target population in this study were: (1) patients with coronary heart disease who indicated coronary artery bypass surgery (CABG) and off pump coronary artery bypass (OPCAB), (2) patients who had heart valve disease indicated by open-valve heart surgery. The target population was patients who underwent adult cardiac surgery at the Division of Adult Cardiac Surgery, RSPJNHK, from October to December 2022.

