3.4. Sample selection method

Sampling in this study was conducted consecutively, including all patients who underwent cardiac surgery in the Division of Adult Cardiac Surgery, RSPJNHK, until reaching the target sample size.

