5.6. Estimated sample size

The number of samples in this study was calculated twice because the dependent variables observed were the amount of bleeding and the need for postoperative blood transfusion, all of which were numerical variables. From the overall calculation results, the largest sample size for this study was taken, then 10% was added to accommodate the possibility of *dropping out*. The formula used in the sample calculation for both variables is the hypothesis test formula for the mean of two independent groups. The literature used as a reference for calculating the sample of this study is a study by Chaudhary et al. (2018).⁴⁴ The following are the sample calculation results for each research variable.

- **A variable amount of bleeding**

$$n_1 = n_2 = 2 \left[\frac{(z_\alpha + z_\beta)s}{(x_1 - x_2)} \right]^2$$
$$n_1 = n_2 = 2 \left[\frac{(1,96 + 0,842)339,021}{300} \right]^2$$
$$n_1 = n_2 = 20,05 \sim 20 \text{ sample}$$

Description:

= normal standard deviation for type I error with α is 0.05 (1.96)

= normal standard deviation for type II error with β is 0.2 (0.842)

= standard deviation between placebo and treatment groups according to the study (placebo = 445.941 mL and treatment = 232.101 mL, so that the mean value taken = 339.021 mL)⁴⁴

= expected clinical difference (taken 300 mL)

- **Variable blood transfusion needs**

$$n_1 = n_2 = 2 \left[\frac{(z_\alpha + z_\beta)s}{(x_1 - x_2)} \right]^2$$

$$n_1 = n_2 = 2 \left[\frac{(1,96 + 0,842)1,072}{1} \right]^2$$

$$n_1 = n_2 = 18,04 \sim 18 \text{ sample}$$

Description:

= average standard deviation for type I error with α is 0.05 (1.96)

= average standard deviation for type II error with β is 0.2 (0.842)

= standard deviation between placebo and treatment groups according to the study (placebo = 1.225 units and treatment = 0.918 units so that the mean value taken = 1.072 units)⁴⁴

= expected clinical difference (taken as 1 unit)

Based on the above calculation results, 20 patients were taken as the minimum sample size for each placebo and treatment group. With the addition of 10% to anticipate dropouts (2 patients per group), the total sample for each group was 22 samples. The total sample for both groups was 44 patients. In this study, there are three arms group (CABG group, OPCAB group, and Valve Surgery group). The total sample for both arms group was 132 patients.

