1.3 Research schedule

| Activities | 2022 | | |
|--|---------|----------|----------|
| | October | November | Desember |
| Submission of research ethics approval | X | | |
| Data collection and retrieval | | X | |
| Data processing and hypothesis testing | | | X |
| Preparation of research report | | | X |

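### The study window, the November-only data-collection schedule and the recruit-to-target rule cannot all hold with 44 patients in each surgery group; the plan must say which governs

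*Combined protocol and SAP*

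**What the plan says.** All references are to the combined protocol and SAP.

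- **Study period.** Section 3.2: "This study occurred from October to December 2022 at the Division of Adult Cardiac Surgery". Section 3.3 places the target population in the same window, "from October to December 2022".
- **Schedule.** The research schedule table (numbered 1.3, after section 3.13) has one column per month. Ethics submission is marked in October. The row "Data collection and retrieval" is marked in November only. Data processing, hypothesis testing and the report are marked in December.
- **End of recruitment.** Section 3.4 takes consecutive patients "until reaching the target sample size".
- **Target.** Section 5.6 sets 22 per arm, hence 44 per surgery group, for three groups: "The total sample for both arms group was 132 patients".
- **Supply.** Section 1.1 gives the hospital's 2020 volumes: coronary artery bypass surgery "with 419 cases", and for valves the hospital "reported 521 patients undergoing heart valve replacement surgery". It gives no OPCAB count, no 2022 volume, and no eligibility or consent rate. Section 1.1.1, speaking generally, says OPCAB demands high skill, "so it is not practised as widely as conventional CABG techniques".

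**The concern.** The plan gives two calendars and one size-based rule for the same recruitment, with no order of precedence. On the protocol's own volumes, the shorter calendar falls far short of the coronary target and the longer one barely covers it. If the study team closes on a date, the CABG and OPCAB comparisons could end well below 22 per arm, and the 80% power in section 5.6 would not describe them. If the team recruits to target, the stated period and schedule are wrong.

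Section 3.4 also does not say whether the target is 132 overall or 44 in each group. Under an overall count, a well-supplied group could fill places while a scarce one stays short.

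**Working it through.** **1. The plan's own sample size.** Inputs from section 5.6: z-values 1.96 and 0.842, SD 339.021 mL, difference 300 mL.

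n per arm = 2 × [(1.96 + 0.842) × 339.021 / 300]² = 20.05, taken as 20. Adding 10% gives 22 per arm, 44 per group, and 22 × 2 × 3 = 132 in total. The stated figure is reproduced. The coronary groups together need 44 + 44 = 88 and the valve group 44.

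**2. Monthly supply.** Assumption: 2020 volumes apply in 2022.

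- Coronary: 419 / 12 = 34.9 per month; 419 / 4 = 104.75 in three months.
- Valve: 521 / 12 = 43.4 per month; 521 / 4 = 130.25 in three months.

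**3. Share of all cases that must be eligible, consent and be randomised.**

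| Need | November only | October to December |
|---|---|---|
| 88 coronary, if 419 includes OPCAB | 88 / 34.9 = 252% | 88 / 104.75 = 84% |
| 44 on-pump CABG, if 419 is on-pump only | 44 / 34.9 = 126% | 44 / 104.75 = 42% |
| 44 valve | 44 / 43.4 = 101% | 44 / 130.25 = 34% |

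If 419 includes OPCAB, three months can fill both coronary groups only if OPCAB makes up between 44 / 104.75 = 42% and 1 − 0.42 = 58% of cases, even with every case enrolled. If 419 is on-pump only, OPCAB feasibility cannot be assessed from the documents.

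**4. Sensitivity to volume.** Doubling the coronary volume gives 2 × 34.9 = 69.8 cases in November, still short of 88. Over three months it gives 209.5 cases, and 88 / 209.5 = 42%.

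**5. Power if recruitment ended on the November schedule.** Assumptions: 419 includes OPCAB, every coronary case is enrolled, and the split is even. Then 34.9 / 4 = 8.7, about 9 per arm in each coronary group.

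Noncentrality = 300 / [339.021 × √(2/9)] = 1.88. The two-sample t-test with 16 degrees of freedom (critical value 2.12) has power 0.42. The normal approximation, which is the plan's own method, gives 0.47. At the planned 20 per arm the same two methods give 0.78 and 0.80.

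**6. Time needed for 88 coronary patients** (419 including OPCAB; the eligible-and-consenting fraction is an assumption): 88 / (34.9 × fraction).

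| Fraction | Months |
|---|---|
| 100% | 2.5 |
| 70% | 3.6 |
| 50% | 5.0 |
| 30% | 8.4 |

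These are totals for the two groups combined. An uneven split would lengthen the time for the smaller group.

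**The case against.** The strongest reply is that section 3.4 already contains the only rule for ending recruitment, and it is size-based. No section says that enrolment closes on a date. The schedule is a four-row, month-level administrative table, and if it slips the power loss does not occur. This stands, and it makes the shortfall conditional. It does not remove the contradiction: section 3.3 puts dates on the population itself, and the schedule has analysis under way in December.

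Four stronger readings are tempting, and the documents do not support them:

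- **That the target is out of reach in October to December.** About 105 coronary cases exceed 88 places, and valve needs about a third of its cases. The valve supply may also be understated, since 521 counts replacements while section 3.5.1 also admits repairs. Impossibility is shown for the coronary groups on the November schedule only, under the stated volume assumptions.
- **That the CABG and OPCAB questions will go unanswered.** That follows only if the calendar overrides section 3.4.
- **That OPCAB is the scarcest group at this hospital.** Section 1.1.1 is a general statement, and no local OPCAB count is given. If OPCAB were a minority of the 419, its group would fall furthest short, but that share is unknown.
- **That patients would be enrolled before ethics approval.** The schedule marks submission in October and gives no approval date. Section 3.11 records approval as granted. October to December can be read as the whole project period.

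The 2020 volumes and the meaning of 419 are real uncertainties. They move the three-month figures a good deal. They do not rescue November: it still falls short for the coronary groups if volume doubled with OPCAB included, and for CABG alone if 419 is on-pump only at 2020 volume.

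**Conclusion.** The point holds as an inconsistency that bears on achieved sample size and power. It does not bias the treatment comparison. Sections 3.2 and 3.3, section 3.4 and the research schedule cannot all be followed while reaching 44 per group.

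On the November schedule, coronary supply is about 35 cases for 88 places, or for 44 if 419 is on-pump only. Closing then would leave at best about 9 per arm in each coronary group and about 42% power for 300 mL, against the planned 80%. Over October to December, the coronary target needs 84% of all cases with a near-even split, before the 15 exclusion criteria and consent are applied. Valve is feasible at 34%.

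The figures assume that 2020 volumes apply in 2022. The 88-place and power figures also assume that 419 includes OPCAB, and the power figure assumes full uptake and an even split.

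**What to change.** - In sections 3.2 and 3.3 and in the research schedule, state that the section 3.4 rule governs and applies per group: starting after ethics approval, each of CABG, OPCAB and valve recruits until 44 patients are randomised.
- Restate the expected duration from the hospital's current volumes, with OPCAB counted separately, and an assumed eligible-and-consenting fraction. On the 2020 figures, with 419 including OPCAB, 88 coronary patients take about 2.5 months at 100% and about 5 months at 50%.
- State that any group closed short will be reported with its achieved size and without the 80% power claim.

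This is an amendment to the text and the schedule. It adds no patients beyond the stated 132 and no procedures. The downside is a longer calendar and later reporting.
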